## 8.1 Safety Data Conventions

Safety data will be handled according to the BMS safety data conventions (described in “Analysis of Safety Data”). This document includes descriptions on how to analyze AE data as well as how to handle partial dates, missing dates, and unknown end dates when analyzing safety data.

## 8.2 Baseline Measurements

For laboratory measures the following will be used, in a hierarchical sequence, to select the baseline (if a criterion does not apply it would be skipped in the sequence):

- The baseline value corresponds to the last lab drawn prior to first dose of study drug;
- If both local and central laboratory values qualify as baseline according to the above criterion, the central laboratory value will be used as the baseline value.

For all other measures (tumor, vital etc.) the baseline value is the last value prior to the first dose of study drug.

## 8.3 Multiple Measurements

### Laboratory Measures

For tabulations of changes from baseline the following will be used, in a hierarchical sequence, to select the post-treatment measurement included in the analysis (if a criterion does not apply it would be skipped in the sequence):

- If multiple laboratory measurements are obtained within the same scheduled time frame, then the measurement obtained on the time closest to the target time/day will be used;
- If more than one value meets the above criterion, then the measurement obtained on the earlier time will be used;
- If both local and central laboratory values qualify as baseline according to the above criterion, the central laboratory value will be used as the baseline value;
- If more than one value meets the above criterion, then the average value will be used.

For tabulations by CTC grade and summarized by worst toxicity grade, if multiple laboratory measurements are obtained within a analysis period (post-baseline), then the worst measurement within the analysis period, respectively, will be used.

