5.4.1.2 Secondary Efficacy Assessment: IMWG Response

Modified IMWG Response criteria in [Appendix 3](#) will be used for the efficacy analysis. All response and progression categories require 2 consecutive assessments to confirm response and progression before initiation of any new therapy. For the purposes of this study, all subjects' tumor assessments by myeloma laboratory tests (SPEP M protein and UPEP M protein quantification, corrected calcium (calcium and albumin), and serum free light chain) should be re-evaluated per the protocol-stated frequency relative to the date of first dose of study drug until disease progression based on [Appendix 3](#), irrespective of dose delays or treatment cycle. **If subject does not have documented disease progression as defined in [Appendix 3](#) at the time**

of study drug discontinuation, then tumor assessments must continue to be performed according to the same schedule described above until disease progression even if a subsequent anti-myeloma treatment is initiated prior to disease progression. Subjects will be followed every 12 weeks, or more frequently, after disease progression for survival, subsequent myeloma therapy, and, for subjects treated with pomalidomide, development of second primary malignancy.

All efficacy laboratory assessments (SPEP, UPEP, serum/urine immunofixation, and sFLC) should be done through the central laboratory for subjects in Cohort B, except for corrected calcium (serum calcium and serum albumin) which will be done locally. Bone marrow assessments for plasma cell percentage and light chain restriction (clonality by IHC or flow cytometry) will be done locally per institution standard practice. For any SPEP, UPEP, or sFLC assessment performed locally, in lieu of a central laboratory assessment, (ie, if the subject cannot complete a visit at the study site), M protein absolute quantification (eg, g/dL or mg/24 hrs) in serum and urine or sFLC (eg, mg/L or mg/dL) must be performed. Any laboratory samples analyzed locally, including for efficacy, must be entered on the appropriate CRF/eCRF as requested by the Sponsor to properly assess efficacy per protocol criteria.

Subjects in Cohort A will have all efficacy assessments performed at the local laboratory.

Laboratory Assessments for Multiple Myeloma

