5.10 Results of Central Assessments

All myeloma efficacy laboratory assessments in Cohort B should be performed by the central laboratory. Investigative site staff will receive reports of the results on an ongoing basis for treatment decisions and patient management throughout the study. Any laboratory samples analyzed locally, including those for efficacy, must be entered on the appropriate CRF/eCRF as requested by the Sponsor to properly assess efficacy per protocol criteria.

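### SAP 8.3's central-over-local clause is worded for baseline and ranks third, so when a Cohort B window holds both, a local or averaged on-study M-protein or sFLC value can be tabulated against a central baseline

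*SAP*

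**What the plan says.** SAP 8.3 (Laboratory Measures) opens its list this way: "For tabulations of changes from baseline the following will be used, in a hierarchical sequence, to select the post-treatment measurement included in the analysis". A criterion that does not apply is skipped. The four steps are, in order:

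1. Among several values in one scheduled window, "the measurement obtained on the time closest to the target time/day will be used".
2. If values are still tied, "the measurement obtained on the earlier time will be used".
3. "If both local and central laboratory values qualify as baseline according to the above criterion, the central laboratory value will be used", and the sentence ends by naming it as the baseline value.
4. "If more than one value meets the above criterion, then the average value will be used".

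Step 3 repeats the second bullet of SAP 8.2. There it follows the baseline definition: "The baseline value corresponds to the last lab drawn prior to first dose of study drug".

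On the source of the data, Protocol 5.10 says "All myeloma efficacy laboratory assessments in Cohort B should be performed by the central laboratory", and Protocol 5.4.1 bases SPEP, UPEP and sFLC on central results, with Cohort A handled locally. Protocol 5.4.1.2 nevertheless provides for local testing ("For any SPEP, UPEP, or sFLC assessment performed locally, in lieu of a central laboratory assessment"), for example when a subject cannot complete a site visit. Sections 5.4.1.2 and 5.10 both require local efficacy results to be entered on the CRF. SAP 7.5 tabulates changes or percent changes from baseline in the serum and urine tests, and plots individual percent changes in M-protein or sFLC.

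**The concern.** The list selects on-study values, and no on-study value can qualify as baseline. Taken literally, step 3 is always skipped, so nothing gives the central laboratory priority after first dose. The position of the step is a second problem: closeness and earliness are settled before the laboratory is looked at.

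Both kinds of result can be in the Cohort B database. A change from baseline may then combine a central baseline with a local value, or with a mean of two laboratories. Part of the tabulated change would be a difference between laboratories rather than a change in disease. This departs from the protocol's intention that these tests rest on central results.

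**Working it through.** The documents give no figure on this point, so there is none to reproduce. The check applies the rule to each pattern of samples that a window can hold.

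**Inputs from the documents.** The four-step order (SAP 8.3); baseline as the last pre-dose value, central if both laboratories qualify (SAP 8.2); central results as the intended source, with local results allowed and recorded (Protocol 5.4.1, 5.4.1.2, 5.10).

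**Illustrative assumptions, not in the documents.** Central baseline 2.0 g/dL; central on-study value 1.0 g/dL; local value = 1.0 × (1 + b), with b = −20%, −10%, +10% or +20%.

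**Formula.** Percent change = 100 × (selected value / 2.0 − 1). The central-to-central change is 100 × (1.0 / 2.0 − 1) = −50%.

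- Local selected, b = ±20%: the value is 0.8 or 1.2, giving −60% or −40%.
- Local selected, b = ±10%: the value is 0.9 or 1.1, giving −55% or −45%.
- Average of both, b = ±20%: the value is 0.9 or 1.1, giving −55% or −45%.
- Average of both, b = ±10%: the value is 0.95 or 1.05, giving −52.5% or −47.5%.

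Three forms of the rule were compared, over b from −20% to +20%:

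| Samples in the window | As written | Step 3 reworded for on-study values, same rank | Central chosen first |
|---|---|---|---|
| Local nearer to target | local, −60% to −40% | local, −60% to −40% | central, −50% |
| Equidistant, local earlier | local, −60% to −40% | local, −60% to −40% | central, −50% |
| Same time | average, −55% to −45% | central, −50% | central, −50% |
| Central nearer to target | central, −50% | central, −50% | central, −50% |
| Local only | local, −60% to −40% | local, −60% to −40% | local, −60% to −40% |

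**General size.** If r is the true ratio of on-study to baseline value, the error in percentage points is 100 × r × b when the local value is chosen and half of that when the two are averaged. For an unchanged subject (r = 1) and a difference of 10 to 20% in size, this is 10 to 20 points, or 5 to 10 points. In the example (r = 0.5) it is 5 to 10 points, or 2.5 to 5 points.

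Two results follow. Correcting only the word in step 3 repairs exact-time ties and nothing else. A window with only a local value is the same under all three forms, so its order of steps is irrelevant and it needs its own rule.

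**The case against.** The strongest reply is that this is a copying slip with an obvious meaning. The clause sits in a list for post-treatment values, and the parallel vital-signs list has the same other steps without it, so it was evidently added to prefer central results. On that reading, averaging across laboratories does not occur. This stands for exact ties, which are needed for averaging in any case. It does not help when the local sample is nearer or earlier.

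The protocol also does not plan duplicate tests. Local testing replaces central testing, so most windows should hold one value. This stands: the conflict is probably infrequent, and no rate is given.

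Three stronger readings are tempting, and the documents do not support them.

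- A reader might infer that a laboratory difference would be counted as a response. SAP 7.5 has ORR in these cohorts assessed by the investigator, and SAP 4.2.2 takes investigator-reported BOR from the CRF. Nothing links 8.3 to ORR, DOR or PFS. Worst-grade safety tables have their own selection rule.
- A reader might infer that the fault bites mainly at missed site visits. Those windows normally hold only a local value, so 8.3 has nothing to choose between.
- A reader might infer that 8.2 needs the same reordering. It is a coherent rule as it stands. Exclusion criterion 2(j)(iv) requires baseline M-protein to be drawn after any short emergency steroid course, and an unrestricted central-first baseline could reach back to an earlier sample.

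Finally, SAP 8 invokes EmBARC windowing and counting standards that are not in the documents. A central-priority rule there cannot be excluded, but it would not override the explicit text of 8.3.

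**Conclusion.** The point holds in a narrow form. SAP 8.3 gives no working central preference for on-study values. Where a Cohort B subject has local and central SPEP, UPEP or sFLC results in one window, the rule can set a local or averaged value against a central baseline, contrary to Protocol 5.4.1.

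The reach is the descriptive change summaries of serum and urine M-protein and sFLC in Cohort B. The spider plots are included only if they use the same selection, which the SAP does not state. Cohort A is tested locally throughout and is not exposed. The error per affected value follows directly from the assumed 10 to 20% difference between laboratories; the true difference and the number of affected windows are unknown. This is a worthwhile clarification, not a threat to the trial's conclusions.

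**What to change.** In SAP 8.3, for SPEP, UPEP and sFLC in Cohort B:

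- Make the laboratory the first step: where local and central values both fall in the same scheduled window, keep the central ones.
- Apply closeness to target, earlier time and averaging only within the laboratory so chosen, so that no average crosses laboratories.
- Use a local value only where the window has no central value, and flag it in the tables and listings.
- Remove the baseline wording from this list, and say whether the spider plots follow the same selection.

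Leave SAP 8.2 as it is. Immunofixation need not be included, because it is a qualitative test with no change-from-baseline tabulation of its own.

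The cost is a few lines of SAP text and a small programming change. The central value may lie a few days further from the target day than the local one it displaces.

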### Vital Signs

The following criteria will be used, in a hierarchical sequence, to select the post-treatment measurement included in the analysis:

- If multiple vital sign measurements are obtained within the same scheduled time frame, then the measurement obtained on the time closest to the target time/day will be used;

- If more than one value meets the above criterion, then the measurement obtained on the earlier time will be used;
- If more than one value meets the above criterion, then the average value will be used.

## 9 CONTENT OF REPORTS

NA

■

[REDACTED]

■

[REDACTED]

■

[REDACTED]
